5.1 Post-Operative Study Calendar

	Post-Op 1-4 weeks	Post-Op 2- 8 weeks	Every 6 mo Years 1-5 ^F	Once per year Years 1-5
Medical History/Demographics	X			
Clinical Breast Exam	X		X	
Physical Exam (including vitals, height & weight)	X			
Prior & Concomitant Medications ^G	X			
Performance Status	X			
Adverse Event Assessment	X			
Adjuvant Therapy		X ^{A, C}		
Endocrine Therapy		X ^B		
Adjuvant Radiation		X ^D		
Mammogram				X ^E

- A. Adjuvant therapy should begin 2-8 weeks following the last surgery date.
- B. Standard adjuvant endocrine therapy of treating physician's choice is administered for 4.5 years. Participation in other adjuvant trials is permitted.
- C. The choice and regimen of adjuvant chemotherapy is at the discretion of the treating physician. Participation in other adjuvant trials is permitted
- D. Administration of whole breast radiation, rather than partial breast or brachytherapy, is recommended for patients in whom adjuvant radiation is indicated.
- E. Patients with breast tissue remaining will undergo annual mammograms of both breasts.
- F. The timing of the office visit and imaging is also documented if recurrence is suspected.

- G. Concomitant medications will be reviewed at each study visit, only prohibited concomitant medications will be entered into the CRFs

6.0 STUDY PROCEDURES

6.1 Screening/Baseline Procedures:

Assessments performed exclusively to determine eligibility for this study will be done only after obtaining informed consent. Assessments performed for clinical indications (not exclusively to determine study eligibility) may be used for baseline values even if the studies were done before informed consent was obtained.

All screening procedures must be performed within 21 days prior to registration unless otherwise stated. The screening procedures include:

6.1.1 Informed Consent

6.1.2 Medical history

Complete medical, surgical and oncology history is obtained at screening. Any changes from Screening (e.g. worsening severity or abnormal findings) are considered to be adverse events (AEs).

6.1.3 Demographics

Demographic profile will include date of birth, gender, race, and zip code.

6.1.4 Review subject eligibility criteria

Review of eligibility criteria as described in Section 3 to ensure subject qualification for study entry.

6.1.5 Review previous and concomitant medications

All prior medication taken by the subject within 4 weeks before starting the study is to be recorded. Concomitant medications taken by the subject during the study are to be recorded up until 30-days after last study dose. If a reportable adverse event (see Section 7) occurs within 30-days after last study dose, recording of concomitant medications should continue until resolution of the adverse event.

6.1.6 Physical exam including vital signs, height and weight

Vital signs (temperature, pulse, blood pressure), height, weight

6.1.7 Performance status (APPENDIX A): Performance status evaluated prior to study entry

6.1.8 Adverse event assessment

Baseline assessment of subject status for determining adverse events. See Section 7 for Adverse Event monitoring and reporting.

6.1.9 Hematology

Hematology to include hemoglobin (Hgb), platelets, total white blood cell count (WBC), and differential.

6.1.10 Serum chemistries

Comprehensive metabolic panel (CMP) to include: albumin, alkaline phosphatase, ALT/SGPT, AST/SGOT, BUN, creatinine, electrolytes (sodium, potassium, calcium, chloride, bicarbonate), glucose, total bilirubin, magnesium, and phosphorus. PT/INR.

6.1.11 Serum fasting lipid panel

6.1.12 Urinalysis

6.1.13 Tumor Biopsies for research: See Section 9.0 for details

6.1.14 Blood draw for correlative studies: See Section 9.0 for details.

6.1.15 Tumor assessment

- Using a standard cm calibrated caliper, measuring tape or ruler, the longest axis and the perpendicular axis of the tumor are to be measured and recorded in metric notation. Baseline evaluation should be done no more than 21 days prior to initiation of study therapy.
- Baseline mammogram, MRI and ultrasound of the diseased breast must be completed within 42 days of registration. MRI must include bi-dimensional breast tumor measurements. Mammogram of the contralateral breast is required to be within 12 months unless a mastectomy was performed.

6.1.16 Other: ECG, Echocardiogram.

6.2 Day 14 (+7 days) of Cycle 1 (28 day cycle): Tumor Biopsies for research and calculation of Ki67.

6.3 Day 1 (+/-7 days) of Cycle 3 (28 day cycle): MRI of the breast for response assessment.

6.4 Days 1 (+/-3 days) of Cycle 2-6 (28 day cycle):

6.4.1 Physical exam including vital signs, height and weight

6.4.2 Performance status (APPENDIX A): Performance status evaluated at every cycle.

6.4.3 Adverse event assessment: See Section 7 for AE monitoring and reporting.

6.4.4 Hematology

Hematology to include hemoglobin (Hgb), platelets, total white blood cell count (WBC), and differential.

6.4.5 Serum chemistries

Comprehensive metabolic panel (CMP) to include: albumin, alkaline phosphatase, ALT/SGPT, AST/SGOT, BUN, creatinine, electrolytes (sodium, potassium, calcium, chloride, bicarbonate), glucose, and total bilirubin. PT/INR

6.4.6 Urinalysis

6.4.7 Serum fasting lipid profile (Cycle 4 only)

6.4.8 Tumor assessment

Using a standard cm calibrated caliper, measuring tape or ruler, the longest axis and the perpendicular axis of the tumor are to be measured and recorded in metric notation.

6.4.9 Drug compliance assessment (Participant Pill Diary Review): Letrozole and ribociclib/placebo medication diary is to be used.

6.4.10 Echocardiogram, when clinically indicated

6.4.11 Special consideration at the beginning of cycle 6: In order for the blood counts to be adequate for surgery and for the importance of continuing therapy until the last day prior to surgery (for accurate Ki67 assessment), ANC should be $\geq 1500/\mu\text{L}$ and platelet count should be $\geq 100,000/\mu\text{L}$ on day 1 of cycle 6. If ANC is < 1500 and platelet count is $< 100,000$ on day 1 of cycle 6, resumption of cycle 6 will be delayed until the recovery of the counts. Growth factor support with filgrastim may be used at the discretion of the

treating physician for ANC <1500 to help with the recovery of the counts at surgery.

6.5 At completion of study treatment – (Days 8-22 of Cycle 6):

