There will be no letrozole dose reductions. If unanticipated grade 3 or 4 toxicity is encountered, which is considered at least possibly related to letrozole, the patient will be discontinued from letrozole therapy. Missed doses of letrozole are not made up.

4.5 Dose modifications and management of toxicity for Ribociclib/Placebo:

For severe adverse reactions the following dose reduction guidelines will be used:

ARM B (Intermittent dosing arm)	Ribociclib/Placebo	
	Dose	Number of capsules
Starting dose	600 mg	3 x 200 mg capsules
First dose reduction	400 mg	2 x 200 mg capsules
Second dose reduction	200 mg	1 x 200 mg capsule
Discontinue	NA	NA

ARM C (Continuous dosing arm)	Ribociclib/Placebo	
	Dose	Number of capsules
Starting dose	400 mg	2 x 200 mg capsules
First dose reduction	200 mg	1 x 200 mg capsule
Discontinue	NA	NA

If a patient discontinues ribociclib/placebo, she will continue on study taking letrozole alone.

If a patient requires a temporary hold of study drug on Day 1 of a cycle, Day 1 will be delayed until patient restarts study drug. There is no need to repeat all procedures listed for Day 1 in Section 5.0.

4.5.1 Ribociclib/Placebo dose adjustment and management recommendation for related hematological adverse reactions:

Toxicity/Grade	Dose Adjustment and Management Recommendations
Thrombocytopenia	
Grade 1 ($\geq 75,000$ /uL)	No dose adjustment required.
Grade 2 (50,000/uL - < 75,000/uL)	Dose interruption until recovery to $\geq 75,000$ /uL. Re-initiate ribociclib/placebo at the same dose.
Grade 3 (25,000/uL - < 50,000/uL)	Dose interruption until recovery to grade $\geq 75,000$ /uL. Re-initiate ribociclib/placebo at the same dose level. If toxicity recurs at grade 3: temporary dose interruption until recovery to $\geq 75,000$ /uL and reduce ribociclib/placebo to the next lower dose level.
Grade 4 (< 25,000/uL)	Dose interruption until recovery to $\geq 75,000$ /uL. Re-initiate ribociclib/placebo at the next lower dose level. If toxicity recurs at grade 4: discontinue ribociclib.
Absolute neutrophil count (ANC)	
Grade 1 ($\geq 1,500$ /uL)	No dose adjustment required.
Grade 2 (1,000 - < 1,500/uL)	No dose adjustment required.
Grade 3 (500 - < 1,000/uL)	Dose interruption until recovery to > 1,000/uL. Re-initiate ribociclib/placebo at the same dose level. If toxicity recurs at grade 3: temporary dose interruption until recovery to > 1,000/uL and reduce ribociclib/placebo dose to the next lower dose level.

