4 QT/QTcF ≥ 501 or > 60 ms change from baseline and Torsades de pointes or polymorphic ventricular tachycardia, or signs/symptoms of serious arrhythmia	
Discontinue ribociclib/placebo
 
 Obtain local cardiologist consultation Perform a repeat ECG one hour after the first QTcF of ≥ 501 ms 
If QTcF remains ≥ 501 ms, repeat ECG as clinically indicated, but at least once a day until the QTcF returns to < 501 ms.

4.5.6 Management of All Other Related Adverse Reactions:

Consider performing an analysis of serum potassium, calcium, phosphorus, and magnesium, for all adverse reactions that are potentially associated with electrolyte imbalance (e.g. diarrhea, nausea/vomiting). If the electrolyte values are below the lower limit of normal, interrupt ribociclib administration, correct electrolytes with supplements as soon as possible, and repeat electrolyte testing until documented normalization of the electrolytes.

4.6 Surgery:

4.6.1 Schedule: Surgery should be scheduled during days 8-22 of the 6th cycle of neoadjuvant endocrine therapy. Protocol therapy will be continued until the day before surgery.

Note: A surgical delay beyond the time frame described above, requires a discussion with the principal investigator or co-investigator. Given the subject population (older with co-morbid illnesses) it may be appropriate for a subject to remain on the endocrine agent to allow a delay in surgery to allow a recovery from inter-current illness for example. These issues will be dealt with on a case-by-case basis.

4.6.2 Breast surgery: The type of breast surgery (either mastectomy or lumpectomy) is determined by the treating surgeon according to institutional standard, with the goal to

completely excise the tumor. A negative margin is required unless further excision is not possible.

4.6.3 Lymph node surgery: The type of lymph node surgery (sentinel lymph node with or without axillary lymph node dissection) will be determined by the treating surgeon according to institutional standard.

4.6.4 Surgical pathology report: Size of the breast tumor; number of lymph nodes examined and the number of positive by H&E staining; final tumor margins; and extent of surgery should be reported with submission of surgical and pathology reports.

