6.5.1 Hematology

Hematology to include hemoglobin (Hgb), platelets, total white blood cell count (WBC), and differential.

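### Section 6.4.11 sets a target for each blood count on day 1 of cycle 6 but delays the cycle only when both are low, so mild single-count cytopenias have no required action.

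*Combined protocol and SAP*

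**What the plan says.** Section 6.4.11 (special consideration at the start of cycle 6) gives two reasons for a count check. One begins "In order for the blood counts to be adequate for surgery". The other is that therapy should run up to surgery so that Ki67 is measured accurately. It then sets a target for each count on day 1 of cycle 6: ANC at least 1500/uL and platelets at least 100,000/uL.

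The next sentence gives the consequence, "resumption of cycle 6 will be delayed until the recovery of the counts", but the condition attached is ANC below 1500 **and** platelets below 100,000. A final sentence makes filgrastim optional, leaving it to the "treating physician for ANC <1500 to help with the recovery of the counts at surgery". That sentence carries no platelet condition.

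The related rules are:

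- **4.5.1, neutrophils.** The row beginning "Grade 2 (1,000 - < 1,500/uL" requires no dose adjustment. For grade 3 (500 to below 1,000/uL) the rule is "Dose interruption until recovery to > 1,000/uL. Re-initiate ribociclib/placebo at the same dose level".
- **4.5.1, platelets.** No adjustment at 75,000/uL or above. Below that, dosing is interrupted until 75,000/uL is reached.
- **4.5.** If study drug is on hold on Day 1 of a cycle, "Day 1 will be delayed until patient restarts study drug".
- **4.6.1.** Surgery falls on days 8-22 of cycle 6, and "Protocol therapy will be continued until the day before surgery".
- **6.5.1.** A blood count is taken in that window ("Hematology to include hemoglobin (Hgb), platelets, total white blood cell count (WBC), and differential"), with no threshold or action attached.

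**The concern.** The target fails when either count is low. The delay applies only when both are low. The negation of 'A and B' is 'not A or not B', so the trigger does not match the target it is meant to enforce. The filgrastim sentence acts on low ANC alone, which suggests that a single low count was meant to matter.

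Two things are at stake, both named by the section itself. The first is readiness for surgery, which follows within three weeks. The second is continuous dosing before the surgical Ki67. A patient who starts cycle 6 at ANC 1,000-1,499 and then drops below 1,000 must have ribociclib/placebo held under 4.5.1 shortly before surgery, which is the situation the section tries to avoid. Surgical Ki67 of 2.7% or less is one component of PEPI 0, the primary endpoint (2.4). Such holds would be expected mainly on ribociclib.

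**Working it through.** The plan gives no figure to reproduce. The check is an enumeration of the rules.

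**Inputs.** Target: ANC ≥1500 and platelets ≥100,000 (6.4.11). Delay trigger: ANC <1500 and platelets <100,000 (6.4.11). Hold thresholds: ANC <1,000 or platelets <75,000 (4.5.1). Release levels: ANC >1,000 and platelets ≥75,000 (4.5.1). Surgery: days 8-22 of cycle 6 (4.6.1).

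**Step 1. Cross the bands.** These thresholds cut each count into three bands, so 3 × 3 = 9 combinations on day 1 of cycle 6, read literally:

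| ANC (/uL) | Platelets <75,000 | Platelets 75,000-99,999 | Platelets ≥100,000 |
|---|---|---|---|
| <1,000 | delayed by 6.4.11 | delayed by 6.4.11 | held by 4.5.1 only |
| 1,000-1,499 | delayed by 6.4.11 | delayed by 6.4.11 | **no required action** |
| ≥1,500 | held by 4.5.1 only | **no required action** | target met |

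**Step 2. Count.** 9 − 1 = 8 combinations miss the target. Of these, 4 are delayed by 6.4.11, 2 are held only by 4.5.1, and 2 have no required action: 4 + 2 + 2 = 8.

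**Step 3. Follow the two cells held only by 4.5.1.** The hold moves Day 1 (4.5) but ends at the 4.5.1 release level. The shortfall against the 6.4.11 target is up to 1,500 − 1,000 = 500/uL for ANC and 100,000 − 75,000 = 25,000/uL for platelets. On the moved Day 1 the same two-count trigger applies. A patient whose other count is adequate can therefore restart in one of the no-action cells.

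**Step 4. Time left before surgery.** 8 − 1 = 7 days to 22 − 1 = 21 days after day 1 of cycle 6.

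**Step 5. Which cell is likely.** In the 10 patients given ribociclib 600 mg with letrozole, neutropenia of any grade occurred in 90% (8.2) and was the only grade 3 or 4 toxicity, in 50% (1.6). Thrombocytopenia is not among the events listed at 10% or more (8.2). The sample is small, but it points to isolated low ANC as the usual case and to both counts being low as the unusual one.

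**Step 6. Apply the correction.** With 'or', the trigger is the exact complement of the target: all 8 failing combinations lead to delay.

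**The case against.** The strongest reply is that the paragraph should be read as a whole. The target sentence already covers each count, and the filgrastim sentence treats low ANC alone as needing recovery, so a site could reasonably delay either patient. That shows the probable intent, but other sites may follow the delay sentence literally, and handling would then differ across a multi-center trial.

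Other points, and what stands of each:

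- **The target is worded as advice.** True: it is softer than a strict requirement. It is still the level that the delay sentence exists to enforce.
- **A Day 1 moved under 4.5 must meet 6.4.11 again.** It must, but it meets the same two-count trigger, so the gap remains.
- **There are backstops.** Filgrastim is discretionary and delays nothing. The count in the surgical window has no threshold. The 4.5.1 hold below 1,000 acts only after the fall has happened. Surgical delay can be discussed case by case (4.6.1), but that does not prevent a late hold.
- **The harm needs several steps, and a 4.5.1 hold stops only ribociclib/placebo.** This stands. Letrozole continues, and the documents give no size for any effect on Ki67, so no numerical bias is claimed.
- **Cells are not patients.** This stands too. The platelet cell in particular has little support in the early safety data.
- **The benefit may come late.** The interim-analysis paragraph of 16.2 says accrual was nearly complete by the time 60 patients had PEPI data, so the change helps only those who have not reached cycle 6.

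**Conclusion.** The concern holds. Read literally, 6.4.11 leaves two combinations below its own target with no required action: ANC 1,000-1,499 with platelets of at least 100,000, and platelets 75,000-99,999 with ANC of at least 1,500. Two further combinations are held by 4.5.1 but can be released up to 500/uL (ANC) or 25,000/uL (platelets) short of the target.

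The practical weight lies on isolated grade 2 neutropenia. That judgement assumes that the pattern in the 10 early patients carries over to this trial. The frequency on day 1 of cycle 6 is not given, so the number of patients affected is unknown. The impact is modest and operational, bearing on surgical readiness and on continuity of dosing before a component of the primary endpoint. It is worth correcting because the error is clear and the remedy cheap.

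**What to change.** In 6.4.11, change the trigger to: *if ANC is <1500/uL **or** the platelet count is <100,000/uL on day 1 of cycle 6*. Add one sentence stating that, for this day only, the rule overrides both the no-adjustment ranges of 4.5.1 and its release levels (ANC >1,000/uL, platelets ≥75,000/uL). Without that sentence the two sections would conflict.

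The cost is one word and one cross-reference in an amendment, with a memo to sites, applied to patients who have not yet reached cycle 6. The downside is some additional cycle 6 delays, probably concentrated in the ribociclib arms because that is where neutropenia is expected. The section's stated target already implies those delays.

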6.5.1 Hematology

Hematology to include hemoglobin (Hgb), platelets, total white blood cell count (WBC), and differential.

6.5.2 Tumor assessment

Mammogram and ultrasound of the diseased breast. MRI may be obtained at the discretion of the surgeon and must include bi-dimensional breast tumor measurements.

6.5.3 Tumor Biopsies at surgery for research and calculation of Ki67 and PEPI score

See Section 9.0 for details. Required research tumor tissue biopsies can be obtained at the time of surgery. Sample submission for Ki67 and correlative studies is required. Calculation of PEPI score is described in Section 9.

6.5.4 Blood draw for correlative studies: See Section 9.0 for details.

6.6 Discontinuation of therapy for reasons other than treatment completion

See Section 6.8

6.6.1 Physical exam including vital signs, height and weight

6.6.2 Performance Status

6.6.3 Adverse event assessment: See Section 7 for AE monitoring and reporting.

6.6.4 Hematology

Hematology to include hemoglobin (Hgb), platelets, total white blood cell count (WBC), and differential.

6.6.5 Serum chemistries

Comprehensive metabolic panel (CMP) to include: albumin, alkaline phosphatase, ALT/SGPT, AST/SGOT, BUN, creatinine, electrolytes (sodium, potassium, calcium, chloride, bicarbonate), glucose, and total bilirubin. PT/INR.

6.6.6 Urinalysis

6.6.7 Tumor assessment

Using a standard cm calibrated caliper, measuring tape or ruler, the longest axis and the perpendicular axis of the tumor are to be measured and recorded in metric notation.

Mammogram, ultrasound, and MRI of the diseased breast. MRI must include bi-dimensional breast tumor measurements

6.6.8 Drug compliance assessment (Subject Pill Diary Review): letrozole and ribociclib/placebo. Medication diary is to be used. See APPENDIX F.

6.6.9 Tumor Biopsies at surgery for research and calculation of Ki67 and PEPI score

See Section 9.0 for details. Required research tumor tissue biopsies can be obtained at the time of surgery. Sample submission for Ki67 and correlative studies is required. Calculation of PEPI score is described in Section 9.

6.6.11 Blood draw for correlative studies: See Section 9.0 for details.

6.7 Follow-Up:

Subjects who have been registered to the study and signed a consent form, but have withdrawn consent prior to receiving any study therapy will be considered a cancellation. No further follow-up is required.

Subjects who discontinue their assigned neoadjuvant therapy due to progression, treatment refusal, intolerable toxicity, desire for alternative non-protocol therapy or other trials, or are unable/unwilling to undergo surgery will enter the follow-up phase of the study.

After the completion of neoadjuvant endocrine therapy and surgery, subjects will enter the follow-up phase of the study, where they will undergo disease evaluations every 6 months of years 1-5.

6.8 Removal of Subjects from Study Treatment and Study:

Subjects can be taken off the study treatment and/or study at any time by their own request, or they may be withdrawn at the discretion of the investigator for safety, behavioral or administrative reasons. The reason(s) for discontinuation will be documented and may include:

- 6.8.1** Subject voluntarily withdraws from treatment (subject agrees to follow-up)
- 6.8.2** Subject withdraws consent (termination of treatment and follow-up)
- 6.8.3** Subject is unable to comply with protocol requirements
- 6.8.4** Subject demonstrates disease progression
- 6.8.5** Subject experiences toxicity that makes continuation in the protocol unsafe
- 6.8.6** Treating physician judges continuation on the study would not be in the subject's best interest
- 6.8.7** Development of second malignancy (except for basal cell carcinoma or squamous cell carcinoma of the skin) that requires treatment, which would interfere with this study;
- 6.8.8** Lost to follow-up.

If a research subject cannot be located to document survival after a period of 2 years, the subject may be considered "lost to follow-up." All attempts to contact the subject during the two years must be documented.

7.0 ADVERSE EVENTS

7.1 Definitions:

7.1.1 Adverse Event [21 CFR 312.32(a)]

An adverse event means any untoward medical occurrence associated with the use of a drug in humans, whether or not considered drug related.

An adverse event (also referred to as an adverse experience) can be any unfavorable and unintended sign (e.g., an abnormal laboratory finding), symptom, or disease temporally associated with the use of a drug, and does not imply any judgment about causality. An adverse event can arise with any use of the drug (e.g., off-label use, use in combination with another drug) and with any route of administration, formulation, or dose, including an overdose.

This study will use the descriptions and grading scales from Common Terminology Criteria for Adverse Events version 4.03 (CTCAE v4.03) for hematologic and non-hematologic toxicities. Detailed information may be found on the Cancer Therapy Evaluation Program (CTEP) website:

http://ctep.cancer.gov/protocolDevelopment/electronic_applications/ctc.htm

Information for adverse events, whether reported by the subject, directly observed, or detected by physical examination, laboratory test or other means, will be collected, recorded, followed and reported in the CRF as described in the following sections.

Adverse events experienced by subjects will be collected and reported from initiation of study medication, throughout the study, and within 30 days of the last dose of protocol therapy. Subjects who experience an ongoing adverse event related to a study procedure and/or study medication beyond 30 days will continue to be contacted by a member of the study team until the event is resolved, stabilized, or determined to be irreversible by the principal investigator. Study subjects should also be instructed to report any new serious post-study event(s) that might reasonably be related to participation in this study.

Medical conditions/diseases, or cancer related symptoms present before starting study treatment are considered adverse events only if they worsen after initiation of study drug. Adverse clinical events occurring before starting study drug but after signing the informed consent form are to be recorded on the CRF where Medical History/Current Medical Conditions are recorded. All cancer-related symptoms that have occurred in the last 30 days prior to start of study drug must also be recorded on the CRF.

Abnormal laboratory values or test results constitute adverse events only if they induce clinical signs or symptoms, or require therapy. In this case they will be recorded on the Adverse Events CRF, along with the associated signs, symptoms or diagnosis.

As far as possible, each adverse event will also be described by:

- its duration (start and end dates)
- grading of severity
- its relationship to the study drug
- the action(s) taken
- outcome

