In a phase Ib/II, multicenter, study, the combination of ribociclib with letrozole in adult patients with advanced ER+ breast cancer is being studied. Three arms (ribociclib + letrozole, BYL719 + letrozole, ribociclib + BYL719 + letrozole) are included in this study. The primary endpoints of the study are to estimate the MTD(s) and/or RP2D(s) for the 3 combinations. The phase Ib part is followed by a phase II part to compare the clinical efficacy of ribociclib + BYL719 + letrozole compared with ribociclib + letrozole or BYL719 + letrozole. The study is currently in the dose escalation phase Ib part. As of 28-Mar-2014, 17 patients have been enrolled: 10 have been treated with at least one ribociclib dose 600 mg PO daily (3-weeks-on/1-week-off) + 2.5 mg letrozole PO once-daily.

The median age of 10 patients treated with ribociclib was 59 (range: 45–67) years, all the patients were female, and the distribution of ECOG performance status of 0/1 at baseline was 5/5 patients, respectively. Among 10 patients treated with ribociclib, 2 patients were discontinued from the study due to progressive disease and 8 patients were still ongoing. Among 10 patients treated with ribociclib, the only grade 3 or 4 toxicity was neutropenia, which occurred in 50% of the patients.

In addition to the intermittent dosing regimen, continuous dosing of ribociclib at 600 mg, 400 mg, and 300 mg has been evaluated in 18 patients. The median age of patients in continuous dosing schedule was 57 years. Male/female ratio was 5/13. Treatment has been discontinued in 12 patients, only one discontinuation has been due to toxicity and remaining due to disease progression. A total of 5 events meeting the DLT criteria were observed in 5 patients and included grade 3 febrile neutropenia (n=1), grade 3 neutropenia (n=2), grade 4 neutropenia (n=1), grade 3 ALT increase (n=1). In the 5 patients receiving 400 mg continuous dosing, only one patient had grade 3 or 4 neutropenia. (Ribociclib IB Edition 8, 9/7/2015).

Given that the safety and efficacy of letrozole is well-established, the 1:1:1 randomization (letrozole plus placebo vs. letrozole plus continuous dosing of ribociclib vs. letrozole plus intermittent dosing (3-weeks-on/1-week-off) of ribociclib) increases a patient's opportunity of

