7.2.6 Recording Adverse Events and Documentation in eVELOS

All **expected** and **unexpected** adverse events and serious adverse events occurring after the subject has signed the informed consent and has started protocol treatment must be fully recorded in the subject's case record form.

All AEs and SAEs regardless of causality must be entered in the KU implementation of eVELOS, (also often called the Comprehensive Research Information System [CRIS]). All SAEs regardless of causality must be entered into eVELOS within 24 hours. Unexpected and expected adverse events must be entered within 15 days and include: new unexpected adverse events; worsening baseline conditions; clinically significant laboratory findings; disease-related signs and symptoms that were not present at baseline, and any event or findings that the Investigator feels is clinically significant.

Documentation must be supported by an entry in the subject's file. A laboratory test abnormality considered clinically relevant, e.g., causing the subject to withdraw from the study, requiring treatment or causing apparent clinical manifestations, or judged relevant by the investigator, should be reported as an adverse event. Each event should be described in detail along with start and stop dates, severity, relationship to investigational product, action taken and outcome.

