10.3 Safety/Tolerability

Analyses will be performed for all subjects having received at least one dose of study drug. The study will use the CTCAE version 4.03 (<http://ctep.cancer.gov/reporting/ctc.html>) for reporting of adverse events.

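### Sections 6.1.2, 7.1.1 and 7.2.6 conflict on when a laboratory or ECG abnormality is an adverse event, so silent grade 3–4 neutropenia may be recorded at some sites and not at others

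*Combined protocol and SAP*

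**What the plan says.** Four statements in the combined protocol and SAP bear on whether an abnormal laboratory or test result is an AE.

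- Section 7.1.1, general definition: an AE "can be any unfavorable and unintended sign (e.g., an abnormal laboratory finding), symptom, or disease temporally associated with the use of a drug". An abnormal laboratory finding is the section's own example.
- Section 7.1.1, later paragraph: "Abnormal laboratory values or test results constitute adverse events only if they induce clinical signs or symptoms, or require therapy".
- Section 6.1.2 (medical history): any departure from the patient's screening state counts as an AE, and abnormal findings are named among the examples.
- Section 7.2.6: the items that must be entered in eVELOS include "worsening baseline conditions; clinically significant laboratory findings; disease-related signs and symptoms that were not present at baseline". It then describes a clinically relevant laboratory abnormality as, for example, one that leads to withdrawal from the study, or one "requiring treatment or causing apparent clinical manifestations, or judged relevant by the investigator, should be reported as an adverse event".

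On grading, 7.1.1 says: "This study will use the descriptions and grading scales from Common Terminology Criteria for Adverse Events version 4.03". On analysis, section 10.3 gives the safety population and the CTCAE version: "Analyses will be performed for all subjects having received at least one dose of study drug". Neither 10.3 nor 16.2 plans a table of laboratory or ECG grades, and neither names a between-arm safety test.

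**The concern.** The laboratory sentence in 7.1.1 is exclusive: without symptoms or a need for therapy, there is no AE. Much of what the protocol expects of ribociclib at grade 3–4 is a number on a report. Sections 4.5.1, 4.5.2 and 4.5.5 act on platelet counts, ANC, bilirubin, transaminases and QTcF as measured. In most rows the response is to interrupt, reduce or discontinue study drug, and no symptom is required. Section 7.1.1 does not say whether interrupting study drug counts as therapy. Read literally, an abnormality that stops ribociclib need not become an AE.

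The dose rules work from the values themselves, so management of the individual patient does not depend on the AE form. What is at stake is the reported safety profile. Section 8.1 lists no blood-count effects among letrozole's side effects, so under-recording would fall mainly on Arms B and C and would shrink the apparent difference from control. It would also blur the picture between the two ribociclib schedules.

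**Working it through.** The documents give no figure that depends on this rule, so there is none to reproduce. The check has three parts.

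**1. One case under each rule.** Take an asymptomatic grade 3 ANC that receives no treatment and leads to interruption of ribociclib under 4.5.1.

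| Rule | Test | Is it an AE? |
|---|---|---|
| 6.1.2 | Any change from screening, abnormal findings included | Yes |
| 7.1.1, general definition | Unfavorable, unintended sign; a laboratory finding can qualify | Can be |
| 7.1.1, laboratory sentence | Must cause signs or symptoms, or require therapy | No, unless interruption is read as therapy |
| 7.2.6 | Clinically significant or relevant, including by investigator judgement | Yes, if so judged |

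The third row cannot be followed together with the first, nor with the fourth when the investigator judges the value relevant. A silent transaminase rise or QTcF prolongation gives the same pattern.

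The withdrawal trigger in 7.2.6 does not settle the matter. Under 4.5, a patient who discontinues ribociclib/placebo stays on study with letrozole alone. Interruption, reduction and even discontinuation of ribociclib are therefore not named triggers, and reach the AE form only through judgement of significance or relevance.

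**2. Which part of the toxicity is exposed.**

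- Grade 3–4, 600 mg intermittent plus letrozole, 10 patients (section 1.6): "the only grade 3 or 4 toxicity was neutropenia, which occurred in 50% of the patients". All of the grade 3–4 toxicity in this cohort is laboratory-defined.
- Any grade, same cohort (section 8.2). Laboratory terms: neutropenia 9, leukopenia 2, anemia 1, lymphopenia 1, creatinine 1, so 9 + 2 + 1 + 1 + 1 = 14. Other terms: nausea 4, fatigue 3 and twelve terms with 1 each, so 4 + 3 + 12 = 19. Laboratory share: 14/33 = 42%.
- Main adverse reactions listed for ribociclib (sections 1.5 and 8.2): 4 of 12 terms are blood counts (33%), or at most 6 of 12 (50%) if renal toxicity and QT prolongation are added.

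**3. Illustration of size.** Expected patients with grade 3–4 neutropenia = (rate in Arm B × 40) + (rate in Arm C × 40).

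- Arm B: 5/10 = 50% (exact 95% CI 19% to 81%), giving 0.50 × 40 = 20.
- Arm C: 1/5 = 20% on continuous 400 mg, section 1.6 (exact 95% CI 0.5% to 72%), giving 0.20 × 40 = 8.
- Total: 20 + 8 = 28 of 80 = 35%.

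The number recorded under the 7.1.1 laboratory sentence alone is 28 × s, where s is the share symptomatic or treated. The documents do not give s, so it is an assumption:

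| s | Recorded | Of 80 |
|---|---|---|
| 10% | 2.8 | 3.5% |
| 25% | 7 | 8.75% |
| 50% | 14 | 17.5% |

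The only pointer to s is in section 1.6. Among 18 continuously dosed patients, 1 of the 4 neutropenia dose-limiting events was reported as febrile. That group mixed 600, 400 and 300 mg and included 5 men, so it is a weak guide.

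**The case against.** The strongest reply is that 7.2.6 is the operative recording rule. Section 7.1.1 itself says that events found by laboratory test are recorded as the following sections describe. Section 7.2.6 is one of those sections, and it makes entry of clinically significant laboratory findings mandatory with no symptom or therapy condition. In addition, 4.5.1 calls the count-triggered events adverse reactions, and 7.1.2 defines an adverse reaction as an AE caused by a drug. Some events also qualify under every rule: 4.5.4 calls for medical therapy, 4.5.5 for correction of low electrolytes, and 6.4.11 allows filgrastim for a low ANC around cycle 6. Section 6.1.2 sits under medical history and could be read as confined to it.

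Much of this stands. It shows that loss is not certain and that many sites would record these events. It does not remove the conflict: the exclusive sentence is still in force, and the wider rule turns on judgement that can differ between sites in a multi-center trial.

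A reader might infer that the 7.1.1 sentence removes most of ribociclib's expected toxicity. The documents support that only for grade 3–4 events in one 10-patient cohort. At any grade the laboratory share is 42%, and in the main-reaction list it is 33% to 50%. A reader might also apply the 50% rate to all 80 ribociclib patients and reach 40. That rate comes from the intermittent schedule, which only 40 of them receive, and the same section reports 1/5 on continuous 400 mg. Nor is a formal safety comparison biased: section 2 has no safety endpoint, and no between-arm safety test is specified.

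**Conclusion.** The rules contradict each other and should be reconciled. If the 7.1.1 laboratory sentence is followed as written, silent, untreated grade 3–4 neutropenia can be left out of the AE summary even when it changes dosing. Silent transaminase and QTcF abnormalities can be lost in the same way, and no planned laboratory-grade table makes up for it.

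The conflict is certain from the text. The consequence is a site-dependent risk. Its size is illustrative only: about 28 of 80 patients with the event, against about 3 to 14 recorded under 7.1.1 alone. This rests on source samples of 10 and 5 patients, on the assumption that those rates carry over to this population, and on an assumed 10% to 50% symptomatic or treated. The affected output is descriptive; the primary endpoint is untouched.

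**What to change.** Replace the laboratory sentence in 7.1.1 and align 6.1.2 and 7.2.6 with it, so that one recording rule applies. One workable form is to record as an AE every laboratory or ECG abnormality that is CTCAE v4.03 grade 3 or higher, or that leads to interruption, reduction or discontinuation of study drug, with or without symptoms or treatment.

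In 10.3 and 16.2, add tables of worst CTCAE v4.03 grade by arm from the CBC, CMP and ECG data, whatever was entered on the AE form. The study calendar (section 5.0) already schedules these on day 1 of cycles 2–6. Include unscheduled values too: in Arm B a day 1 sample normally follows seven days off ribociclib, whereas in Arm C it does not, so day 1 values alone would not compare the schedules evenly.

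Section 16.2 notes that accrual was almost complete when the first 60 patients had PEPI data. For patients already treated, the tables are therefore the more useful part of the change.

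The cost is amendment wording, some extra AE entries per patient, the programming of the tables, and data entry if the values are not already in the database (the protocol does not say). No new procedure is needed, and no dose or management rule changes.
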